5. To assess pre-trial expectations and post-trial experiences regarding the therapeutic effects of the Zoles insoles and understand their influence on the efficacy of the intervention within the specific subgroup of participants with high baseline pain levels.

Methods

Trial design

The ZOLES trial is a pragmatic, outcome assessor blinded, randomised, controlled, superiority trial, with a two-group parallel design, and a 1:1 allocation ratio. Frequent recreational runners will undergo foot scanning and thereafter be randomised to either receive a customised 3D-printed insole (Zoles ApS, Esbjerg, DK-3060, Denmark), or to be in a “do-as-usual” control group. The pragmatic design and pre-planned secondary analyses are heavily inspired by the SExSI trial [39].

The trial protocol is based on the "PREPARE Trial guide" [35] and adheres to the "SPIRIT 2013 explanation and elaboration: guidance for protocols of clinical trials" [40] and SPIRIT checklist (Appendix A). The trial report will follow the “REPORT guide” [41], and thus adhere to the CONSORT guidelines for reporting parallel group randomised trials [42], using the CONSORT extension for pragmatic trials [43], as well as the updated CONSORT-Outcomes 2022 extension [44]. The TIDieR template (Appendix B) is used to describe the intervention to aid future replication [45].

The study was approved by the St Mary’s University Ethics Sub-Committee on 4 August 2023, and the trial was pre-registered at ClinicalTrials.gov on 4 September 2023 (ID: NCT06034210) [46], before the first participant was enrolled on September 16, 2023.

Study setting

Participant screening and enrolment for this study is undertaken from Faculty of Sport, Technology and Health Sciences at St Mary’s University (Twickenham, London, United Kingdom), with recruitment to the trial being carried out at local parkrun communities, primarily from Bushy Park (Richmond upon Thames, London, United Kingdom).

Eligibility criteria

Inclusion criteria

- a) Participant is ≥ 35 years old at commencement of trial.
- b) Participant can read, speak, and understand English.
- c) Participant can receive e-mails and complete online questionnaires.
- d) Participant is a frequent runner who participate in regular parkrun activities.
- e) Participant is capable of running at commencement of trial.

Exclusion criteria

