The sample size estimation is based on the primary outcome, running-related pain. Lopes et al. [9] reported a median pain level of 3 (IQR: 2-5) among 1049 recreational runners. We expect similar pain levels at baseline which, if normally distributed, should result in a mean pain of 3 and a standard deviation of 2.22 ($SD \approx IQR/1.35$). We forecast a 40% reduction in running-related pain in the intervention group over the course of the trial (from baseline to follow-up). Using the formula $n = (Z_{\alpha/2} + Z_{\beta})^2 * 2\sigma^2/d^2$, where d is the expected difference between groups, to detect a 40% reduction in pain (1.2 units) with 80% power at a 5% significance level, we initially require 70 participants per group [50]. Factoring in an anticipated 15% dropout, this number increases to 82 participants per group. To accommodate the pre-planned secondary subgroup analyses in the future, we further inflate the number by approximately 20%, leading to a total of 100 participants in each group. Hence, this study aims to recruit a cumulative sample size of 200 participants.

Recruitment

Participants are primarily targeted and approached within the local London parkrun communities. Following their routine Saturday 5-km run, a strategic engagement occurs where they will be approached by study representatives. The parkrun offers a natural setting to converse with potential participants who are already involved in regular running activities. During this engagement, participants are presented with an oral briefing about the study, its objectives, and the potential benefits of their participation. This method not only taps into a pool of runners but also allows for immediate interaction, answering any initial queries they might have. Interested runners, eager to contribute or benefit from the study, are subsequently invited to the Biomechanics Laboratory of the Faculty of Sport, Technology, and Health Sciences at St Mary's University in Twickenham, London, UK. Here, they are introduced to

the broader scope of the study, the commitment expected from them, and the potential implications of the research, and ultimately a formal enrolment into the study.

Allocation

Upon completion of the baseline questionnaires, participants will be equally distributed (1:1 ratio) to the two comparison groups (intervention group and “do-as-usual” control group) using a balanced block randomisation method.

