The trial will include prospective data collection using e-mail-distributed surveys via REDCap (Vanderbilt University, Nashville, TN, USA). Participants receive these surveys weekly for the initial 10 weeks, facilitating the collection of real-time data on their experience, pain levels, and the impact of the customised insoles for those in the intervention group. At the conclusion of this primary trial period (week 10), participants in the control group are provided with their customized insoles, marking the commencement of an additional 8-week observation period to compare intervention response between both groups (week 18). The final follow-up occurs at the 52-week mark, again via REDCap to provide insights on their long-term experiences, adverse effects, and the sustained impact of the Zoles insoles on their running-related pain and comfort.

Reminders will automatically be sent to participants at 24 hours and 48 hours after the original time of a follow-up questionnaire to participants failing to respond. Investigators will contact participants via telephone and SMS after another 24 hours if still not responding after receiving reminders to reduce the amount of missing data.

Data management

Every participant is assigned a unique identification number, ensuring their anonymity throughout the study in compliance with the General Data Protection Regulations (GDPR) under the Data Protection Act 2018.

Data collection, both at baseline and throughout the prospective stages, is facilitated via REDCap, a secure and robust online platform renowned for its data management capabilities [56]. This process is overseen from Department of Clinical Medicine at Aalborg University (DK-9220, Aalborg Øst, Denmark) by a dedicated data handler (CD), who remains blinded to group allocation. CD and FGL constitute the Data Monitoring Committee. A list of responding and non-responding participants is generated weekly, wherefrom a list of non-responding participants to contact is generated.

The Study Director (FGL) will maintain a secured key to the participants' identities, stored on a two-factor secured personal drive, ensuring the capability to identify and withdraw individual data if necessary.

All data is safeguarded within GDPR compliant two-factor and password-protected systems at St. Mary's University server, and on the REDCap online system. These measures ensure that the data remains inaccessible to unauthorized personnel, preserving confidentiality.

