Statistical methods – secondary subgroup analysis and post-market surveillance

The subsequent secondary analysis publication will hold the label "secondary and long-term follow-up analysis from a pragmatic randomised controlled trial" in the title. The aims of this secondary subgroup analysis study are two-fold: First, it is to investigate the immediate therapeutic effect of Zoles insoles, focusing only on participants with clinically relevant baseline pain levels (11-NRS ≥ 3) [38]. Secondly, this will include our long-term post-market analysis to evaluate the long-term effects and durability of the benefits associated with the customised 3D-printed insoles one-year post-intervention.

The between-groups difference among participants with clinically baseline pain levels will be analysed similarly to the primary outcome. Subsequent regression models will, however, also be structured to comprehend the potential influence of pre-intervention expectations and post-intervention experiences, as well as adherence to the intervention on the Zoles insoles' effectiveness within this subgroup. This involves incorporating these factors as covariates in the model.

Statistical methods – analysis population and missing data

For the primary and secondary outcomes of this trial, an intention-to-treat (ITT) analysis approach will be employed [58]. This method ensures the inclusion of all randomised participants in the analysis, irrespective of their adherence to the intervention. Participants will be analysed based on their initial randomisation. As such, any deviations from the intervention or missing follow-ups will not impact the participant's initial group classification in the analysis, as recommended by the CONSORT group [42,44].

To accommodate this approach, missing outcome data will be imputed using multiple imputations by chained equations [59]. The imputation procedure will include the following variables pre-hypothesised to potentially predict missing information: a) preceding scores relevant to the outcome in question, b) age of the participant, c) sex of the participant, d) group allocation, and d) location of recruitment (specific parkrun location).

Harms

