Despite these challenges, the study's structure and methodology have been meticulously crafted to yield insights that are both scientifically rigorous and practically insightful, balancing between the ideal conditions for experimental control and the complexities of real-world application. Conversely, this study boasts several strengths that bolster its reliability and validity. The use of blinded group allocation sequence, external outcome assessors who are blinded to the group assignments, and an external data manager also blinded to group allocation ensures objectivity in data collection and analysis, minimizing bias. Furthermore, the recording of all outcomes in participants' natural environments, including baseline data, amplifies the real-world applicability of the findings. Participants are thus not influenced by the study personnel, ensuring the outcomes reflect the real-life effect of the intervention, enhancing the study's external validity. Additionally, the employment of a mobile scanning unit allows us to recruit participants from more distant parkrun locations, thus allowing for enrolment of participants who might not have the means to travel across London to partake in this study.

The intention to treat analysis in the primary study report ensures all participants are included in the final analysis, maintaining the randomisation benefits and offering a conservative estimate of the intervention's effectiveness. The step-wedge design addition enhances the study's robustness, allowing immediate verification of effectiveness by comparing the control group's response post-primary trial period to the intervention. The inclusion of a 52-week post-market surveillance further elevates the study's comprehensiveness, offering insights into the long-term effects and usability of the insoles.

Transparency is maintained through pre-registration of the study and the detailed description of the intervention using the TIDieR checklist [45], ensuring replicability and openness in reporting. The publication of this study protocol underscores the commitment to transparent and ethical research practices, contributing to the broader scientific discourse and public scrutiny.

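### Missing week-10 pain is imputed under missing at random, without adherence data or a sensitivity analysis, so the intention-to-treat estimate is not assured to be conservative for the imputed share

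*Combined protocol and SAP*

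**What the plan says.** Under Statistical methods – analysis population and missing data, all randomised runners are analysed in their allocated group regardless of adherence. To allow this, "missing outcome data will be imputed using multiple imputations by chained equations". The listed predictors are preceding scores for the outcome concerned, age, sex, group allocation and recruitment location.

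Adherence in daily life and during running is a secondary outcome, and the schedule in Figure 3 collects it weekly from week 3. It is not among the imputation predictors, and Statistical methods only describes it. No section plans a sensitivity analysis for missing data.

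The Discussion (Strengths and limitations) credits the intention-to-treat analysis with "maintaining the randomisation benefits and offering a conservative estimate of" the insoles' effectiveness.

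On the expected amount of missing data, Sample size inflates the number per group with the words "Factoring in an anticipated 15% dropout". Procedures and data collection plans reminders at 24 and 48 hours, then telephone and SMS contact.

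**The concern.** The imputation fills in a missing intervention runner from intervention runners with similar earlier scores who did answer. That is right if, given those variables, the missing runners fare like the responders. It is wrong in one direction if they have stopped wearing the insoles and lost the benefit: an analysis of everyone randomised should then count them without it, but the imputation gives much or all of it back.

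This route is plausible here. Participants are unblinded, the primary outcome is self-rated pain, and the protocol itself foresees insoles that do not fit and new injuries. Earlier pain scores are the only listed predictor that could reveal that someone had stopped, because adherence is left out.

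What is at stake is mainly the size of the reported benefit, and whether the Discussion may tell readers that any error lies on the cautious side.

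**Working it through.** **Inputs.** From Sample size: effect 1.2 NRS units (40% of a mean of 3), SD 2.22, dropout 15%, 100 per group. From Trial design: "with a two-group parallel design, and a 1:1 allocation ratio".

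**The plan's own figure.** The plan says "with 80% power at a 5% significance level, we initially require 70 participants per group". Its formula, n = (Z_α/2 + Z_β)² × 2σ²/d², gives (1.960 + 0.842)² × 2 × 2.22² / 1.2² ≈ 53.7, so 54 per group and not 70. (At 90% power it gives 72.) The later steps do follow: 70/0.85 = 82.4, and 82 × 1.2 = 98.4, rounded to 100. The mismatch is in the safe direction and does not bear on this point. Only the 1.2, the 2.22 and the 15% are used below.

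**Simple bound.** Let d be the share of the intervention arm that is missing and f the share of those who lose the benefit.

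- Effect in all randomised = (1 − d·f) × 1.2
- Estimate if the missing are credited with the full effect = 1.2
- Overstatement = d × f × 1.2

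With d = 0.15 and f = 1, the true effect is 0.85 × 1.2 = 1.02 and the overstatement is 0.18, or 0.18/1.02 ≈ 18%. With f = 0.5 it is 0.09, and with f = 0 it is nil. With f = 1 and other dropout rates it is 0.06 (5%), 0.12 (10%), 0.24 (20%) and 0.36 (30%). If the effect is zero, the overstatement is zero.

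**Do preceding scores reduce this?** This was simulated with 200,000 participants, normal weekly scores with SD 2.22, and 15% dropout in both arms. Each week was imputed by regression on group and all preceding scores, and week 10 was compared with adjustment for baseline. Three things are assumed: a week-to-week correlation of 0.3, 0.5 or 0.7; a benefit that starts after week 2 and is full by week 5; and a first missed survey in weeks 4 to 10. The model is linear, not the plan's negative binomial, and omits age, sex and location.

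| Missing intervention runners | True effect | Imputed estimate | Excess |
|---|---|---|---|
| Keep the benefit | 1.19–1.21 | 1.19–1.21 | about 0 |
| Lose it only after the last answered survey | 1.01–1.02 | 1.19–1.20 | 0.17–0.18 |
| Lose it two weeks earlier | 1.02–1.03 | 1.16–1.17 | 0.14–0.15 |
| Never had it | 1.01–1.03 | 1.12–1.15 | 0.11–0.12 |

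A separate simulation at 100 per arm (400 replicates, Monte Carlo standard error about 0.016) gave 1.21 against 1.02 when dropouts reverted to the control course, and a bias of 0.01 with no true effect.

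**Non-adherent responders.** Adding 10% or 20% of responders who stop the insoles but keep answering (correlation 0.5, second row of the table) lowers the true effect to 0.92 or 0.82, and the imputed estimate to 1.08 or 0.96. The excess is about 0.15 to 0.17.

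**Is group in the model the cause?** No. Leaving group out when dropouts keep the benefit biases the estimate by −0.10 to −0.12.

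**Scale.** The unadjusted standard error at 100 per group is 2.22 × √(2/100) = 0.31. Power is about 97% for an effect of 1.20 and about 90% for 1.02.

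**The case against.** The strongest reply is that the harm is assumed. Missing data here means an unanswered e-mail survey. Nothing says that such a runner stops wearing insoles already in hand, and if the benefit continues there is no bias. This stands, and it makes the whole point conditional.

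Second, intention to treat is usually called conservative because non-adherent people who still answer dilute the effect. Their observed scores stay in the analysis, and the imputation borrows from them too. This also stands: the dilution is real. It does not cover the imputed share, where an excess remained after such responders were added.

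Third, 0.18 is the largest value at 15% dropout, it is smaller than the standard error of 0.31, and the planned reminders and calls may reduce missingness. All true, although the plan itself allows for 15%.

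Three stronger readings are tempting but not supported:

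- A reader might infer that group allocation should be taken out of the imputation. It belongs there, as the check shows.
- A reader might infer that controls have to keep answering to obtain insoles, and so drop out less. At week 10, "participants in the control group are provided with their customized insoles", but the text attaches no condition about surveys. In an open-label trial controls could equally drop out more, and the documents give no basis for unequal rates.
- A reader might infer a raised risk of a false-positive result. With no true effect and dropouts following the control course, the bias is nil.

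**Conclusion.** The concern holds in conditional form. The plan imputes week-10 pain under missing at random, leaves out the adherence data it collects, and examines no departure from the assumption. If intervention runners who stop responding also lose the benefit, the difference is overstated by up to 0.18 NRS units (1.20 against 1.02) at 15% dropout and a 1.2-unit effect. The excess is about 0.11 to 0.15 if their earlier scores already show the loss. It is nil if they keep the benefit or if the insoles have no effect.

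A reader might go further and conclude that the estimate is anti-conservative, so that the Discussion has the direction backwards. The documents do not support that, because they do not say what non-responders do with their insoles. The claim of conservatism is unsupported for the imputed share, not refuted. The primary analysis need not change, so this is a cheap improvement. The 15% and the 1.2 are the plan's; the loss of benefit, its timing and the week-to-week correlation are assumptions.

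**What to change.** 1. Keep the planned chained-equation imputation, including group, as the primary analysis.
2. Add weekly adherence, or a record of insole discontinuation, as a predictor in the intervention arm. Controls have no such value before week 10, so it should enter for that arm only. It helps only where stopping was reported before the last answered survey, so it does not replace step 3.
3. Pre-specify two sensitivity analyses, reported beside the primary result and not as a condition on the superiority claim:
   - One control-based imputation of missing intervention-arm week-10 scores, stating how scores recorded before dropout are used.
   - One delta analysis that worsens the imputed intervention-arm scores in steps and reports the tipping point. The team should set the range beforehand; 0 to 2 points would reach the protocol's own minimal clinically important difference. At 15% missing, a delta of 2 moves the difference by 0.15 × 2 = 0.30.
4. In Strengths and limitations, delete the word conservative or attach it only to the control-based estimate.

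The cost is a few sentences of plan wording, a little more analysis code, and a sensitivity estimate that may be less favourable. Ethics and dissemination already provides a route for recording modifications. The change should be made before week-10 results are seen by group.

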No Intervention: “Do-as-usual” control group

Participants allocated to the control group are a "do-as-usual" comparator. This implies, that the participants may treat and prevent running-related pain and discomfort in any way they wish, except using the Zoles 3D-printed insoles.

Outcomes

Primary outcome

The primary outcome will be the change in running-related pain 10 weeks after baseline. Pain, although subjective, is a crucial determinant of runners' quality of life, performance, and continued participation in the activity [13]. For this trial, an 11-NRS pain scale will be utilized, ranging from 0 to 10 (0 = No pain at all, 10 = Worst pain imaginable) [48].

Baseline values for the primary outcome will be collected using online e-mail-distributed surveys via REDCap (Vanderbilt University, Nashville, TN, USA). Running-related pain data will be further collected at weekly intervals, with the focal analysis being between-group changes from baseline to the 10-week mark. The main outcome will be reported as the difference in mean change in running-related pain between the group using Zoles customised 3D-printed insoles and the "do-as-usual" control group, adjusting for values reported at baseline [49].

Secondary outcomes

The secondary outcomes include:

- **Global Rating of Change (GRoC) in overall daily pain and discomfort:** Participants will be asked to self-assess their perceived change in overall daily pain and discomfort relative to their state at the start of the study. They will use a 7-point scale, from -3 ("much worse") to 3 ("much better"), as indicated in the study by Bobos et al. [36] This outcome will be measured weekly until the 10-week mark, and again at the 18-week mark.
- **Running-related foot/footwear comfort:** The change in comfort from the start to the 10-week mark, relating specifically to running and footwear, will be captured using a numeric rating scale ranging from 0 (Extremely uncomfortable) to 10 (Extremely comfortable) based on the parameters defined by Menz & Bonnano [37]. This outcome will be measured at baseline with weekly follow-up measurements until the 10-week mark, and again at the 18-week mark.

- **5k-completion time:** The time taken by participants to complete their weekly 5 km parkrun will be recorded weekly, providing insights into any performance changes over the trial period.

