- **Running-related injuries:** The incidence rate of injuries related to running will be monitored and reported as the number of injuries for every 1000 hours of running exposure over the 10-week duration.
- **Time-loss:** The total number of days participants miss out from running due to pain, discomfort, or injury will be tracked weekly for 10 weeks, and again at the 18-week mark.
- **Weekly Mileage:** The distance participants run every week will be recorded during the 10-week trial period, and again at the 18-week mark.
- **Weekly running exposure:** The total time participants spend running every week will be obtained in hours and minutes for the 10-week trial period, and again at the 18-week mark.
- **Adherence to intervention, ADL%:** This outcome tracks how frequently participants use the Zoles insoles for everyday activities such as sitting, standing, walking, and driving over the 10 weeks, and tracked again at the 18-week mark, and at the 52-week post-market surveillance.
- **Adherence to intervention, RUN%:** The percentage of time participants wear the Zoles insoles specifically during running will be monitored over the 10 weeks, and again at the 18-week mark, and at the 52-week post-market surveillance.
- **Adverse events from using Zoles insoles:** All adverse events associated with the usage of Zoles will be reported based on their type and number. Throughout the trial, participants will be encouraged weekly to report any adverse events through the trial

hotline. Participants will be asked again at the 52-week-post-market-surveillance to capture any long-term events.

Other Outcomes

The other outcomes of interest for the pre-planned secondary subgroup analyses include:

- **Participants achieving MCID reduction in pain:** This measure looks at the percentage of participants who manage to achieve a clinically meaningful reduction in running-related pain, defined as a reduction equal to or larger than the MCID (NRS \geq 2) as described by Salaffi et al. [48] over the 10 weeks.
- **Time until MCID reduction in pain:** This outcome gauges the time in weeks it takes for participants with clinically significant pre-existing pain (NRS \geq 3 as defined by Rathleff et al. [38]) to achieve the clinically meaningful reduction in running-related pain (MCID) during the 10-week trial period.

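### The imputation list for week-10 pain omits the weekly injury, time-loss, running-time, GRoC and comfort data, so the contrast can be biased if injury-related missingness differs by arm

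*Combined protocol and SAP*

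**What the plan says.** All references are to the Combined protocol and SAP.

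- **Method.** Under Statistical methods – analysis population and missing data, "missing outcome data will be imputed using multiple imputations by chained equations".
- **Variables.** The same section continues: "The imputation procedure will include the following variables pre-hypothesised to potentially predict missing information". The items are "preceding scores relevant to the outcome in question, b) age of the participant, c) sex of the participant, d) group allocation", and finally the parkrun where the participant was recruited.
- **Outcome.** "The primary outcome will be the change in running-related pain 10 weeks after baseline" (Primary outcome). "Running-related pain data will be further collected at weekly intervals", so up to nine follow-up scores precede week 10.
- **Data collected but not listed.** Secondary outcomes defines time-loss as "The total number of days participants miss out from running due to pain, discomfort, or injury", tracked weekly. Weekly running time, GRoC and comfort are there too. Figure 3 schedules all of these, and running-related injuries, at each of weeks 1 to 10.
- **Collection.** Procedures and data collection describes a weekly e-mailed survey, with reminders at 24 and 48 hours and then telephone and SMS contact.

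The plan states no missing-data assumption and no sensitivity analysis for missing data.

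**The concern.** The primary outcome is pain related to running. A participant who stops running because of pain or injury may have no such pain to rate, or may stop answering. The weekly time-loss, injury and running-time items are the data that would identify such a person, and GRoC and comfort carry further information on current state. The list is presented as the expected predictors of missing information, yet names none of them. The phrase "preceding scores relevant to the outcome in question" reads most naturally as earlier values of the same outcome.

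Imputation is unbiased only if, given the variables in the model, missingness does not depend on the unseen score. If injury drives both and is left out, injured participants are filled in with scores that are too low. When this happens equally in both arms it cancels from the contrast. When it does not, it remains.

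Unequal arms are possible here. Blinding states that participants know their group, and Secondary objectives lists injury incidence and time-loss among the outcomes that the insole may change. Statistical methods itself names a new injury as a potential effect modifier.

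**Working it through.** The plan gives no figure for this point, so there is none to reproduce. The check asks how large the bias could be, and when it vanishes.

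**From the documents (Sample size):** planned difference 1.2 points, SD 2.22, anticipated dropout 15%.

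**Assumed, since the documents give no values:** injury proportion p (control 20% or 25%, insole 10%); pain added by injury J (2 or 3 points); proportion missing at week 10 among the injured q (70% or 40%) and among the uninjured r (6%). With p = 20% v 10% and q = 70%, missingness is 0.20×0.70 + 0.80×0.06 = 18.8% in control and 0.10×0.70 + 0.90×0.06 = 12.4% with insoles. The average is 15.6%, close to the plan's 15%.

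**Step 1: earlier pain scores carry no sign of the injury.** This applies if the injury starts in week 10, or if the score is blank from onset. Imputed values then follow the observed members of the arm:

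- injured share among the observed: p_obs = p(1−q) / [p(1−q) + (1−p)(1−r)]
- error in the arm mean: J × (p_obs − p)
- error in the contrast: insole error minus control error

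For 20% v 10%, q = 70%:

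- control: p_obs = 0.060/(0.060 + 0.752) = 0.0739; error = −0.1261 J
- insole: p_obs = 0.030/(0.030 + 0.846) = 0.0342; error = −0.0658 J
- contrast: +0.0603 J, which is 0.12 at J = 2 and 0.18 at J = 3

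For 25% in control, p_obs = 0.075/(0.075 + 0.705) = 0.0962 and the error is −0.1538 J. The contrast error is +0.0880 J, which is 0.18 or 0.26. The planned difference is a reduction, so a positive error shrinks the benefit.

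**Step 2: earlier scores do reflect the injury.** Large simulations used baseline, group and all nine preceding weekly scores, with linear imputation and injury starting in weeks 7 to 10. Injured participants kept reporting pain until week 10.

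| Injury (control v insole), J | Step 1, q = 70% | Step 2, q = 70% | Step 2, q = 40% |
|---|---|---|---|
| 20% v 10%, +2 | 0.12 | 0.10 | 0.05 |
| 20% v 10%, +3 | 0.18 | 0.13 | 0.06 |
| 25% v 10%, +2 | 0.18 | 0.14 | 0.06 |
| 25% v 10%, +3 | 0.26 | 0.19 | 0.08 |
| 15% v 15% | 0.00 | 0.00 | 0.00 |

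If the score is blank from onset and onset falls in weeks 6 to 10, the four unequal rows give 0.13, 0.19, 0.19 and 0.28 at q = 70%, even with all nine scores in the model. Across the runs the range is about 0.04 to 0.28 points: 0.04/1.2 = 3% to 0.28/1.2 = 23% of the planned difference.

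**Step 3: equal injury, unequal missingness.** With injury 20% in both arms, J = 2, r = 8%, and 60% v 20% of the injured missing, the bias is 0.09 to 0.16. The lower figure applies when the preceding score reflects the injury.

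**Step 4: what the omitted data recover.** In Step 2 at q = 70%, adding week-9 injury status leaves 0.03 to 0.07, so about two thirds is removed. If the injury starts in week 10, week-9 status removes nothing. Same-week status brings the bias close to zero, but only where it is observed.

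**The case against.** **The bias is conditional, and the conditions are assumed.** This stands. A reader might infer that the omission by itself biases the primary result. The documents do not support that: they give no injury rate, no missingness by arm and no link between the two. With like arms the error cancels.

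**Nine earlier pain scores already do much of the work.** Partly right. They reduce the bias when injured participants go on reporting pain. They do not help when the score goes blank at onset or the injury is new in week 10.

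**The list does not exclude other variables.** True of the wording, and the first item could be read loosely. But injury counts and running hours are not naturally earlier scores of pain, and a prespecified list should not depend on a generous reading.

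**The omitted variables are lost with the same survey.** This stands, and it limits the repair. A reader might infer that adding them removes the bias. That holds only for surveys returned with pain alone blank. Reminders and telephone contact should reduce missed surveys, but cannot be assumed to remove them.

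**The direction is conservative.** In the scenarios run the error shrinks the benefit. It would reverse if insoles increased injury.

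**Non-runners might be scored zero.** A reader might infer this, because the text gives no rule for a week without running. The weekly questionnaire (Appendix G) is listed by title only, so nothing shows how such weeks are scored. That is a question of outcome definition, not of the imputation list, and no size is claimed for it here.

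**Conclusion.** The point holds in conditional form. The list omits five collected weekly variables that plausibly bear on both missingness and pain, and no sensitivity analysis covers the gap. If injury or injury-related missingness differs by arm, the week-10 contrast can be off by about 0.04 to 0.28 NRS points toward no benefit, against 1.2 planned. That rests on assumed injury of 20-25% v 10%, 2 to 3 added pain points, and 40-70% of the injured missing. With like arms it is about zero. The calculation works with differences in means and linear imputation; the plan's negative binomial model was not simulated. The correction is inexpensive and worth making before the data are analysed.

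**What to change.** 1. In the chained-equations model for week-10 pain, add the preceding weeks' time-loss, injury, running time, GRoC and comfort. Add their week-10 values where the survey was returned with only pain blank.
2. State that these are auxiliary variables for imputation only. The Statistical methods section keeps effect modifiers such as new injury out of the intention-to-treat analyses, and this change does not put them into the analysis model.
3. Add a delta-adjusted sensitivity analysis in which the shift to imputed pain scores may differ by arm. With 15% missing in each arm, shifts of d₁ (insole) and d₀ (control) move the contrast by about 0.15 × (d₁ − d₀). A 2-point shift in control alone moves it by 0.15 × 2 = 0.30.
4. Report missing week-10 pain by arm, split into whole survey missed and pain item alone blank.

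No new data are needed. The cost is a slightly larger imputation model and one more sensitivity analysis. With 200 participants and ten weeks of several variables, the earlier weeks may need summarising, for example as the latest value and a running total.
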